8.2. Handling of Missing and/or Unquantifiable Immune Response Data

Missing immune response data will not be imputed.

Depending on the assay, a lower limit of quantification (LLOQ) will be available or a provisional cutoff will be set at the analysis level. Values below the LLOQ or cut-off will be treated as follows:

- Values will be imputed based on the type of analysis. For the calculation of the geometric mean titer, values below LLOQ will be imputed to LLOQ/2. While for the calculation of the geometric mean of the increase from baseline, values below LLOQ will be imputed to LLOQ. The LLOQ values per assay are available in the database.
- For ICS assays: no valid LLOQ is available. A provisional cut-off is put at 0.02%. (only for total cytokine response). For the individual cytokine combinations of IFN γ , TNF α and IL2, negative values will be imputed with 0. For descriptive statistics or graphs on actual values, values below the cut-off will be imputed to a value of cut-off/2. For Th1 and Th2, a provisional cut-off of 0.001% is used. These values might change in the future, depending on progressing insight. For descriptive statistics or graphs on actual values, values below the cut-off will be imputed to a value of cut-off/2.
- For all assays: values above the upper limit of quantification (ULOQ) will be imputed with 2xULOQ.

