 - symptoms from two different categories (Upper Respiratory, Lower Respiratory, Systemic) from the SSC, regardless of grade and assessment timepoint *OR*
 - any Grade 2 symptom from any category.
 - Liberal (RT-PCR): two or more quantifiable RT-PCR measurements plus any clinical symptom of any severity from the SSC.

The SSC categories are defined as follows:

- *Upper Respiratory symptoms*: runny nose, stuffy nose, sneezing, sore throat, earache
- *Lower Respiratory symptoms*: cough, shortness of breath, chest tightness, wheeze
- *Systemic symptoms*: malaise, headache, muscle and/or joint ache, chilliness/feverishness

Note: the quantifiable RT-PCR assessment and the symptoms should not necessarily occur at the same day.

The **exploratory efficacy** endpoints are the following:

- Proportion of subjects with symptomatic RSV infection based on RT-PCR or serology. Symptomatic RSV infection is defined as:
 - Liberal (RT-PCR or Serology): the subject has two or more quantifiable RT-PCR measurements or serology confirmation of RSV (4-fold increase in G a or G b Elisa, 28 days after challenge), and any clinical symptom of any severity.
- AUC of the total clinical symptom score. The AUC for the total clinical symptom score will be calculated based on equation (1). In case the first and/or last time point is missing, it will be set to zero, no other missing time point will be imputed.
- Clinical symptom scores per item over time
- Respiratory parameters measured by spirometry:
 - Forced expiratory volume in 1 second (%) – FEV1
 - Forced vital capacity (%) – FVC
 - FEV1/FVC Ratio (%) – FEV1/FVC

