8.3.1.1. Humoral assays

For VNA and ELISA assays, if available, following results will be calculated: N, geometric mean[§] and corresponding 95% CI of the actual values and fold increases from baseline will be tabulated and graphically presented. [§]*calculate the mean and corresponding 95%CI of the log₂ transformed values, back-transform this mean [i.e. 2^{mean}] and CI [i.e. 2^{CI}].*

Tables showing fold increases will also present the percentage of subjects with an x-fold increase (for several values of x).

Actual values and fold changes from baseline are tabulated and shown as dot plots with dots for subject values, and the corresponding geometric mean and 95% CI per time point for each assay. In addition, GMT plots over time, combining the regimens in one graph (without individual subject dots) will also be created.

Ratios of actual values and of fold changes from baseline between humoral assays may also be presented.

Subject profiles of the actual values over time will be graphically presented.

Reverse distribution curves of the actual values are provided for selected time points.

In the graphs, original values will be displayed on the log₂ scale.

Scatterplot with humoral assays may be provided for the most important time points. In these scatter-plots the actual values will be shown, even if they are below the LLOQ, but the LLOQ cut-off will be visualized in the graph per assay if some values are below LLOQ.

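### For fold rises, setting titres above the upper limit to twice that limit can count a demonstrated rise of little more than 2-fold as a 4-fold response

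*SAP*

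**What the plan says.** SAP 8.2 handles unquantifiable immune response data. At the lower limit the rule depends on the use. For titres: "For the calculation of the geometric mean titer, values below LLOQ will be imputed to LLOQ/2". For fold rises: "for the calculation of the geometric mean of the increase from baseline, values below LLOQ will be imputed to LLOQ". At the upper limit there is a single rule for all assays, whatever the analysis: "values above the upper limit of quantification (ULOQ) will be imputed with 2xULOQ".

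Three outputs depend on fold rises.
- SAP 8.3.1.1 reports geometric mean fold increases, computed on the log scale ("calculate the mean and corresponding 95%CI of the log₂ transformed values", then back-transformed).
- SAP 8.3.1.1 also plans responder percentages: "Tables showing fold increases will also present the percentage of subjects with an x-fold increase (for several values of x"). The values of x are not fixed.
- SAP 6.2 defines the exploratory Liberal (RT-PCR or Serology) endpoint. With any symptom, infection may be confirmed by two quantifiable RT-PCR results or by a "4-fold increase in G a or G b Elisa, 28 days after challenge". SAP 8.1 lists the G/N ELISA among the humoral assays, so the all-assays rule reaches it; SAP 6.2 gives no separate rule.

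The lower-limit rule for fold rises is worded for the geometric mean of the increase only. The SAP does not say whether it also governs the x-fold percentages or the 4-fold G-ELISA call. Neither document gives ULOQ values, retesting at higher dilution, a count of values above ULOQ, or a sensitivity analysis for the upper-limit rule.

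**The concern.** A value above ULOQ shows only that the titre exceeds ULOQ. Doubling it credits the subject with a further factor of two that was not measured, and creates a jump exactly at the limit. For a fold rise, that factor goes straight into the ratio. At the lower limit the SAP avoids this kind of credit by using LLOQ rather than LLOQ/2 when it computes increases; at the upper limit it does not.

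At stake is whether a recorded x-fold or 4-fold rise means that such a rise was demonstrated. For the G-ELISA call, a symptomatic subject could be classed as having RSV infection on serology without a demonstrated 4-fold rise.

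**Working it through.** The plan attaches no sample size, power or significance level to these outputs, so there is no stated figure to reproduce. Write U for ULOQ, b for a quantifiable baseline and y for the true later value, with y > U. SAP 3.1 sets the immunogenicity baseline at the last value before vaccination. SAP 6.2 does not name the reference sample for the G-ELISA rise, but the arithmetic is the same for any reference.

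**1. When a 4-fold call is not demonstrated.** Recorded rise = 2U/b. Demonstrated rise = U/b (the true rise is somewhat above this). True rise = y/b.
- Recorded as at least 4-fold: 2U/b ≥ 4, so b ≤ U/2.
- Not demonstrated as 4-fold: U/b < 4, so b > U/4.

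The window is therefore U/4 < b ≤ U/2. Within it the call is wrong if y < 4b and right if y ≥ 4b. For a general threshold x the window is U/x < b ≤ 2U/x.

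With y = 1.05U:

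| b/U | true (1.05/b) | recorded (2/b) | with ULOQ (1/b) |
|---|---|---|---|
| 0.25 | 4.2 | 8.0 | 4.0 |
| 0.30 | 3.5 | 6.67 | 3.33 |
| 0.40 | 2.62 | 5.0 | 2.5 |
| 0.50 | 2.1 | 4.0 | 2.0 |
| 0.75 | 1.4 | 2.67 | 1.33 |
| 0.90 | 1.17 | 2.22 | 1.11 |

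The rows at 0.30, 0.40 and 0.50 are false 4-fold calls. The rows at 0.75 and 0.90 would be false calls at x = 2.

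**2. The error depends on how far y lies above U.** With b = U/2 the recorded rise is always 4.0. The true rise is 2.1, 3.0, 4.0, 6.0 and 8.0 for y = 1.05U, 1.5U, 2U, 3U and 4U. The rule overstates below 2U and understates above it.

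**3. The lower limit, for comparison.** With true baseline LLOQ/4 and later value 4 × LLOQ, the true rise is 16-fold. It is recorded as 4-fold under the LLOQ rule and would be 8-fold under LLOQ/2. The LLOQ rule is conservative for rises.

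**4. Baselines above ULOQ.** These are doubled too. Two values above ULOQ give a ratio of 1.0. A fall from 1.05U to 0.9U is truly 0.9/1.05 = 0.86, but is recorded as 0.9/2 = 0.45.

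**5. Geometric mean fold rise.** Each later value above ULOQ is one log2 unit higher under the SAP rule than under a ULOQ rule, if the baselines are quantifiable. With k such values among 22 subjects (the planned arm size in SAP 1.4), the two rules differ by 2^(k/22): 1.03 for k = 1 and 1.17 for k = 5. This is the gap between two conventions, not a bias against the truth.

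**6. Geometric mean titres.** Assume log-normal titres with share p above ULOQ and log2 standard deviation s; both are assumptions. The mean log2 excess above ULOQ is e = s(φ(z)/p − z), where z is the upper-p normal quantile. Imputed over true GMT is 2^(p(1−e)) under the SAP rule and 2^(−pe) if ULOQ is used.

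| | p = 10% | p = 25% | p = 50% |
|---|---|---|---|
| SAP rule, s = 1 | 1.04 | 1.07 | 1.07 |
| SAP rule, s = 2 | 1.00 | 0.97 | 0.81 |
| ULOQ rule, s = 1 | 0.97 | 0.90 | 0.76 |

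The bias of the SAP rule can go either way. The ULOQ rule always understates the GMT.

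**The case against.** Four objections deserve weight.

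**The rule is symmetric for titres.** On the log scale, 2 × ULOQ mirrors the LLOQ/2 used for geometric mean titres. Replacing it by ULOQ there would create an asymmetry and bias the GMT downwards. This stands, and is why the point is confined to fold rises and responder calls.

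**The window needs a high baseline.** Subjects are selected for low neutralising titres to the challenge strain (Protocol 3.1 and 4.1), which makes such baselines less likely in that assay. This stands for that assay; it does not settle the matter for the F or G ELISAs.

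**The efficacy link is narrow.** The serology route changes a subject's status only if there are symptoms, fewer than two quantifiable RT-PCR results, a baseline in the window and a later value above ULOQ. Nothing in the documents shows that such a subject will occur.

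**The alternative has its own error.** Some subjects in the window truly reach 4-fold and would be lost under a ULOQ rule. This stands as a cost.

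A reader might also infer that the rule inflates vaccine-arm GMTs and so overstates the vaccine–placebo contrast. The documents do not support that. The direction of the GMT bias depends on a spread and a share above ULOQ that they do not give. The rule covers both arms and all visits. More vaccine-arm values above ULOQ are plausible for F-directed assays, but this is not shown, and it does not carry over to G, which Protocol 2.1.2 treats as an antigen outside the vaccine.

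**Conclusion.** The point holds for fold rises and responder calls. The upper-limit rule can record a 4-fold rise where only a 2-fold to under-4-fold rise is demonstrated, and it lacks the safeguard that the SAP builds into its lower-limit rule for increases. The error is misclassification of individual subjects, possible in either arm, for baselines above ULOQ/4 and at or below ULOQ/2 (with the corresponding window for other values of x). For geometric mean fold rises the case rests on consistency with the lower-limit rule, since the average bias against the truth can have either sign.

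How many subjects are affected cannot be worked out from the documents, and may be none. The consequences are limited to descriptive immunogenicity outputs, for which no hypothesis is tested (SAP 8.3), and to one exploratory efficacy endpoint. The primary VL-AUC analysis has its own imputation rule in SAP 6.1.1 and is untouched. Applying the rule to the G-ELISA call rests on reading all assays in SAP 8.2 as covering the assays listed in SAP 8.1.

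**What to change.** In SAP 8.2, add that for geometric mean fold rises, x-fold percentages and the 4-fold serology call in SAP 6.2, values above ULOQ are set to ULOQ and values below LLOQ to LLOQ. State explicitly that both limits apply to responder calls. A later value above ULOQ then counts as an x-fold response only if ULOQ/baseline reaches x; in the example with baseline ULOQ/2 and a true 2.1-fold rise, 2.0 is recorded instead of 4.0. Report the number of values above ULOQ by assay, arm and visit.

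Leave the rule for geometric mean titres as it is. At most, add a censored log-normal GMT as a sensitivity analysis.

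The cost is a short addition to the SAP and one count table. The downside is that some genuine 4-fold rises with later values above ULOQ will be counted as non-responses, and reported fold rises become slightly less favourable. The counts above ULOQ show how far that can matter.

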8.3. Immune Response Analysis

No formal hypothesis on immunogenicity will be tested.

8.3.1. Immunogenicity against the insert:

8.3.1.1. Humoral assays

For VNA and ELISA assays, if available, following results will be calculated: N, geometric mean[§] and corresponding 95% CI of the actual values and fold increases from baseline will be tabulated and graphically presented. [§]*calculate the mean and corresponding 95%CI of the log₂ transformed values, back-transform this mean [i.e. 2^{mean}] and CI [i.e. 2^{CI}].*

Tables showing fold increases will also present the percentage of subjects with an x-fold increase (for several values of x).

Actual values and fold changes from baseline are tabulated and shown as dot plots with dots for subject values, and the corresponding geometric mean and 95% CI per time point for each assay. In addition, GMT plots over time, combining the regimens in one graph (without individual subject dots) will also be created.

Ratios of actual values and of fold changes from baseline between humoral assays may also be presented.

Subject profiles of the actual values over time will be graphically presented.

Reverse distribution curves of the actual values are provided for selected time points.

In the graphs, original values will be displayed on the log₂ scale.

Scatterplot with humoral assays may be provided for the most important time points. In these scatter-plots the actual values will be shown, even if they are below the LLOQ, but the LLOQ cut-off will be visualized in the graph per assay if some values are below LLOQ.

8.3.1.2. Cellular assays

For ICS and PBMC secreted cytokines, if available, analyses may include:

Total Cytokine response: the % of subsets expressing at least IFN γ , TNF α or IL2 will be calculated for CD4 and CD8, separately.

For total cytokine responses, tables with number of observations, median, first and third interquartile per timepoint will be provided.

Subject profiles of the actual values over time will be graphically presented.

Actual values are shown as box plots with dots for subject values, and the corresponding median and the first and third quartile (Q1, Q3) per time point.

In addition, box plots over time, combining the regimens in one graph (without individual subject dots) will also be created.

For all cytokine combinations (IFN γ and/or TNF α and/or IL2) pie charts reflecting the distribution of each of the cytokine combinations (the proportion of a specific cytokine combination of the CD4 or CD8 T-cells secreting at least one cytokine) and bar charts reflecting the median magnitude of each combination will be graphically presented. Tables with the corresponding descriptive statistics will be provided.

Th1 and Th2: Th1 is defined as all CD4+ IFN γ + and Th2 as all CD4+ IL4+ cells. Subject profiles and graphs of the actual values over time (box-plot type) will be created. In addition, at time points of interest, scatterplots of Th1 vs Th2 might be created.

For the graphs, original values will be displayed on the log₁₀ scale.

The technical details for the calculation of the ICS values to be used in the graphs will be outlined in the DPS.

For **ELISpot**, if available following results will be calculated: N, median, quartiles and range of the actual values will be tabulated and graphically presented per timepoint.

Subject profiles of the actual values over time will be graphically presented.

Actual values are shown as box plots with dots for subject values, and the corresponding median and interquartile range per time point for each assay. In addition, box plots over time, combining the regimens in one graph (without individual subject dots) will also be created. For the graphs, original values will be displayed on the log₁₀ scale. Scatterplot with humoral and cellular assays may be provided for the most important time points.

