1.1. Background

RSV is considered to be the most important cause of serious acute respiratory illness in infants and children under 5 years of age.^{16,34,38} Globally, in 2005, RSV was responsible for an estimated 3.4 million hospitalizations worldwide in children under 5 years of age. Furthermore, 66,000 to 199,000 children younger than 5 years died from RSV-associated acute lower respiratory tract infection (LRTI) in 2005, and 99% of these deaths occurred in developing countries.²⁷ Nevertheless, the disease burden due to RSV in developed countries is substantial, with RSV infection during childhood linked to the development of wheezing, airway hyperreactivity and asthma.^{31,33,35,36,37} In the United States (US), the infection rate was 68.8% in children younger than 12 months of age and 82.6% during the second year of life. Virtually all children had been infected at least once by 24 months of age, and about one half had experienced 2 infections.¹⁴ In the US, RSV infection in children under 5 years of age is the cause of 57,000 to 175,000 hospitalizations, 500,000 emergency room visits, and approximately 500 deaths each year.^{30,34,38} In children under 1 year of age, RSV is the most important cause of bronchiolitis, and RSV hospitalization is highest among children under 6 months of age.^{6,16}

In addition to children, RSV is an important cause of respiratory infections in the elderly, immunocompromised, and those with underlying chronic cardiopulmonary conditions.¹⁰ In long-term care facilities, RSV is estimated to infect 5-10% of the residents per year with significant rates of pneumonia (10 to 20%) and death (2 to 5%).¹¹ In one epidemiology study of RSV burden, it was estimated that 11,000 elderly persons die annually of RSV in the US.³⁹ These data support the importance of developing an effective vaccine for certain adult populations.

Despite the high disease burden, no licensed vaccine is available for RSV. The first vaccine candidate for young children, which consisted of formalin-inactivated RSV (FI-RSV), was associated with enhanced respiratory disease (ERD) upon infection with RSV.¹⁹ Although the mechanisms for ERD are not fully understood, it is thought that FI-RSV failed to induce adequate neutralizing antibody titers and CD8 priming, and induced a T-helper (Th) 2 skewed response.²⁶

Adenoviral-vectored Vaccines

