- Pre-F antibody in nasal wash samples measured by pre-F enzyme-linked immunosorbent assay (ELISA) normalized to a standard protein or antibody to account for variability of sample volume, dilution and concentration in nasal wash samples.
- Proportion of subjects with symptomatic RSV infection (RT-PCR or serology). Seroconversion is defined as a four-fold rise against the G and/or N protein by ELISA which would indicate a take of the virus inoculum to such extent that a systemic immunologic response against an antigen not in the vaccine was induced.
- Neutralizing antibody against RSV-Memphis 37b (challenge strain) and RSV A2.
- RSV pre-F and post-F antibodies from serum and nasal wash samples^a measured by ELISA.
- Respiratory parameters: spirometry (FEV1, FVC, FEV1/FVC).

^a Assumes that the ELISA for nasal wash samples will be available.

- Vaccine immune response defined as specific pre-F levels of antibody as measured by ELISA, specific neutralizing antibody levels, F antigen-specific cellular responses as measured by interferon gamma enzyme-linked immunospot (IFN γ ELISpot) assay, flow cytometry cytokine analysis and/or secreted cytokines compared to placebo.

Additional exploratory analyses may be performed to investigate vaccine-elicited immune responses further. These may include, but are not limited to, the following assays:

- RSV cross-neutralization of B and/or other A strain
- Binding antibodies to RSV G and/or N
- F-protein antibody specificity characterization
- Adenovirus neutralization assay
- Functional and molecular antibody characterization

Refer to Section [9.2](#) for evaluations related to endpoints.

Objectives and endpoints are tabulated in [Attachment 2](#).

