
 To explore the immune response of a single dose of 1×10^{11} vp of Ad26.RSV.preF compared to placebo. 	
 Evaluation of vaccine-specific responses before challenge by F-protein specific humoral responses measured by binding and/or VNA, and increase in cellular responses as measured by ELISpot and/or ICS.

 To explore humoral and cellular responses to challenge with RSV-A Memphis 37b in immunized and non-immunized subjects. 	
 ELISA (pre-F, total), neutralization, cellular (IFN ELISpot, flow cytometry).

 Additional exploratory analyses may be performed to investigate vaccine-elicited immune responses further. 	
 RSV cross-neutralization of B and/or other A strain. F-protein antibody specificity characterization. Adenovirus neutralization assay. Functional and molecular antibody characterization.

 To explore other potential efficacy endpoints, as defined in the SAP, to determine the best efficacy endpoint to use in subsequent clinical studies investigating the vaccine's efficacy. 	

Note: Symptomatic RSV infection is defined as two quantifiable RT-PCR measurements at different timepoints

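### Protocol Attachment 2 names the increase in cellular response as an endpoint, but Protocol 11.5 and SAP 8.3.1.2 plan only per-timepoint values, so the increase is never quantified (minor, cheap to fix)

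*SAP*

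**What the plan says.** The documents describe the cellular endpoint and its analysis in four places.

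- **Protocol Attachment 2.** The objective is the immune response to a single dose, with placebo as comparator. The endpoint covers vaccine-specific responses before challenge, including the "increase in cellular responses as measured by ELISpot and/or ICS".
- **Protocol 2.1.2 (and the synopsis).** The endpoint is "F antigen-specific cellular responses as measured by interferon gamma enzyme-linked immunospot", with "flow cytometry cytokine analysis and/or secreted cytokines compared to placebo". Placebo is the comparator here too, but an increase is not mentioned.
- **Protocol 11.5.** ELISpot and ICS are summarised by median and quartiles at all timepoints. Fold rises from baseline are mentioned for humoral assays only, as optional.
- **SAP 8.3.1.2.** For ELISpot, "N, median, quartiles and range of the actual values will be tabulated and graphically presented per timepoint". For ICS, "For total cytokine responses, tables with number of observations, median, first and third interquartile per timepoint will be provided". Subject profiles over time and box plots are also planned, all on actual values.

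For the humoral assays, SAP 8.3.1.1 goes further: the geometric mean and "corresponding 95% CI of the actual values and fold increases from baseline will be tabulated and graphically presented", together with the percentage of subjects reaching given fold increases.

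SAP 3.1 defines an immunogenicity baseline (the last value before vaccination) and lists it as a summarised timepoint. Protocol 9.2.1 collects a cellular sample before vaccination, another one or two days before challenge, and another 28 days after challenge.

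**The concern.** If the plan is followed as written, the Attachment 2 endpoint is not produced as a number. There is no within-subject change, no fold change and no arm contrast for any cellular assay, although the samples needed are drawn. The difference between two timepoint medians does not replace it, because in general it is not the median of the within-subject changes.

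Baseline matters here because subjects are not RSV-naive. Protocol 1.1 reports, from US data: "Virtually all children had been infected at least once by 24 months of age". Entry screening (Inclusion Criterion 5) selects on neutralizing antibody only, so subjects may differ widely in F-specific T-cell memory before vaccination. A post-vaccination value mixes that memory with the vaccine response.

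The stake is interpretive. Protocol 1.1 says an efficacious RSV vaccine should induce CD8+ and Th1-type CD4+ T-cell responses. Protocol 1.2 would read a null result, with no trend in the other endpoints, as evidence against the challenge model. That reading is stronger if the report can show how large a cellular response the vaccine produced.

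**Working it through.** **Text comparison.** An increase is named in Attachment 2 only. Sections 2.1.2 and 11.5 do not require it, and SAP 8.3.1.2 matches 11.5. The mismatch therefore starts inside the protocol and the SAP inherits it.

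**Size.** The plan states no precision or power for cellular endpoints, so there is no figure to reproduce. The calculation below shows scale only.

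Inputs:
- 22 per arm (Protocol 11.2; SAP 1.4), which counts challenged subjects.
- Between-subject SD on the log10 scale: not in the documents; assumed 0.5, range 0.3 to 0.7, equal at both timepoints.
- Correlation r between baseline and post-vaccination values: not in the documents; assumed 0.7, range 0.5 to 0.9.

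Standard error of the between-arm difference on the log10 scale, with n per arm:
- actual values: SD × √(2/n)
- change from baseline: SD × √(2(1 − r)) × √(2/n)
- baseline-adjusted: SD × √(1 − r²) × √(2/n)

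With SD 0.5, r 0.7 and n 22, √(2/22) = 0.3015:
- actual values: 0.5 × 0.3015 = 0.151; margin 10^(1.96 × 0.151) ≈ 1.97-fold
- change: 0.151 × √0.6 = 0.117; margin ≈ 1.69-fold
- adjusted: 0.151 × √0.51 = 0.108; margin ≈ 1.63-fold

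Over the assumed ranges, the adjusted margin is 1.80-fold at r 0.5 and 1.35-fold at r 0.9 (SD 0.5). At r 0.7, the raw and adjusted margins are 1.50 and 1.34 for SD 0.3, and 2.59 and 1.97 for SD 0.7.

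**Which baseline method.** Standard errors in units of one SD, 22 per arm:

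| r | actual values | change | adjusted |
|---|---|---|---|
| 0.3 | 0.302 | 0.357 | 0.288 |
| 0.5 | 0.302 | 0.302 | 0.261 |
| 0.7 | 0.302 | 0.234 | 0.215 |
| 0.9 | 0.302 | 0.135 | 0.131 |

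An unadjusted change is more precise than the raw value only when r exceeds 0.5. In this approximation, adjustment is never less precise.

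**Chance imbalance.** The baseline difference between arms also has standard error 0.151. A 2-fold difference is 0.301 on the log10 scale, so the chance of an imbalance of 2-fold or more in either direction is 2 × (1 − Φ(0.301/0.151)) ≈ 4.6%. It is 0.1% at SD 0.3 and 15% at SD 0.7. About half of it, 2.3% at SD 0.5, would favour the vaccine arm.

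**Carry-over.** With equal SDs, a baseline difference carries into the post-vaccination value in proportion to r. A 2-fold imbalance therefore appears as 10^(0.7 × 0.301) ≈ 1.6-fold at r 0.7, and 1.4-fold at r 0.5.

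**The case against.** The best defence is that the SAP does what the protocol's statistical section asks. Protocol 11.5 chose medians and quartiles for ELISpot and ICS. All immunogenicity is exploratory with no hypothesis tested, and the link to efficacy is only explored graphically. This stands: it makes the point minor, and it means a reader who concluded that the SAP departs from the protocol would be going too far.

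A reader might also infer that pre-existing T cells can bias the vaccine-placebo comparison, hiding or creating an effect. The documents do not support that. Allocation is randomized 1:1 within cohort (Protocol 5), so prior memory adds noise and any imbalance is due to chance. Nor is it right that baseline is ignored: SAP 3.1 summarises it as a timepoint, and the profiles and box plots would reveal a marked imbalance or rise. What they do not give is a size.

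A third tempting reading is that a 2-fold baseline imbalance would look like a 2-fold vaccine effect. That would need a correlation of 1; under the assumptions above it is about 1.6-fold.

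The sample may also exceed 22 per arm, since the PPI set includes vaccinated subjects who are not challenged and Protocol 3.1 allows up to 70 to be vaccinated. At 35 per arm, with SD 0.5 and r 0.7, the margins fall to about 1.7-fold raw and 1.5-fold adjusted. The gain from adjustment remains.

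Finally, SAP 8.2 says ICS has no valid LLOQ, only a provisional cut-off that may change. A log-scale model with values floored at that cut-off is not plainly better than a median. This also stands, and it shapes the fix.

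**Conclusion.** The point holds as an endpoint that is stated but not quantified. Attachment 2 asks for an increase in cellular response, Sections 2.1.2 and 11.5 do not, and SAP 8.3.1.2 supplies none, although baseline samples exist and the SAP tabulates fold increases for humoral assays.

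The consequence is lost precision and exposure to chance imbalance, not systematic bias. On the assumed central values, leaving out baseline widens the 95% margin for the arm ratio from about 1.63-fold to 1.97-fold. These figures rest on an SD and a correlation that the documents do not give; if the correlation is low, little precision is lost. Because the endpoint is exploratory and descriptive, this is a minor point worth correcting because correction costs so little.

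**What to change.** 1. In SAP 8.3.1.2, add for ELISpot and for total CD4 and CD8 ICS responses the within-subject change or fold change from the pre-vaccination sample: N, median and quartiles, by arm and timepoint.
2. State how values below the LLOQ or cut-off enter that change. For ICS, SAP 8.2 gives a half-cut-off rule for actual values but none for change.
3. For the pre-challenge draw (the SAP's 28-days-post-vaccination timepoint), add one active-versus-placebo contrast adjusted for the baseline value, labelled descriptive. Use adjustment rather than a bare change score, because the latter helps only if the correlation exceeds 0.5. Note that the ICS cut-off is provisional, and use a rank-based version if many values fall below it.
4. Align Protocol Attachment 2, 2.1.2 and 11.5 so that they describe the same cellular endpoint and summary.

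A baseline-adjusted ratio for the humoral assays is optional; their fold increases are already tabulated.

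Cost: some SAP and protocol wording, a few descriptive table columns and one simple model per assay. It needs no new samples and uses no alpha.
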